10.3 Early termination assessments

Permanent discontinuation of IMP

Unless the subject discontinues IMP due to withdrawal of consent, lost to follow-up, or death, subjects will be encouraged to continue in the trial for collection of scheduled efficacy and safety assessments, or at least attend an early termination visit and primary endpoint visit as indicated below (see Section 4 for data to be collected at these visits). The investigator will review any AEs which will be followed up according to Section 13.7, if the subject agrees.

Subjects who permanently discontinue IMP prior to Week 16 (Visit 11) will be asked to attend at least:

- Early termination visit, as soon as possible and within 2 weeks of the last IMP administration.
- Primary endpoint assessment visit at nominal Week 16 (Visit 11).

Subjects who permanently discontinue IMP at Week 16 (Visit 11) or hereafter will be asked to attend at least:

- Early termination visit, as soon as possible and within 2 weeks of the last IMP administration.

THIS DOCUMENT CONTAINS CONFIDENTIAL INFORMATION AND MUST NOT BE COPIED OR MADE AVAILABLE TO ANY THIRD PARTY WITHOUT THE PRIOR WRITTEN CONSENT OF THE LEO PHARMA GROUP

Withdrawal from trial

Subjects who withdraw from the trial for any reason will be asked to attend an early termination visit as soon as possible after last administration of IMP. See the schedule of trial procedures (Section 4) for data to be collected. The investigator will review any AEs which will be followed-up according to Section 13.7, if the subject agrees.

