14.3.6 Estimand strategy

14.3.6.1 Overview

For each endpoint associated with a trial objective, a primary estimand will be pre-specified. Additional supplementary estimands will be used to further aid in the interpretation of the results.

For each estimand, pre-specified sensitivity analyses will be conducted to assess the robustness of the results with respect to departures from the statistical assumptions supporting the associated models/estimators.

Description of intercurrent events

An intercurrent event refers to a post-randomisation event that either precludes the existence of or affects the interpretation of the measurements of an endpoint. For the purposes of this trial, we define the following 3 intercurrent events:

Permanent discontinuation of IMP independent of pandemic restrictions: This event occurs when a subject permanently discontinues IMP for reasons not related to COVID-19 pandemic restrictions. Permanent discontinuation of IMP due to sickness with COVID-19 (an AE) will be interpreted as permanent discontinuation of IMP independent of pandemic restrictions. This event can occur either at the subject's own initiative or at the investigator's or sponsor's discretion. The timing of the event will be taken as the date of permanent discontinuation of IMP recorded in the eCRF.

Permanent discontinuation of IMP due to pandemic restrictions: This event occurs when a subject permanently discontinues IMP for reasons related to COVID-19 pandemic restrictions. Permanent discontinuation of IMP due to sickness with COVID-19 (an AE) will not be interpreted as permanent discontinuation of IMP due to COVID-19 pandemic restrictions. Examples of permanent discontinuation of IMP due to pandemic restrictions are quarantines, travel limitations, subject being unable or unwilling to travel to site due to personal pandemic-related reasons, site closures, reduced availability of site staff, and interruptions to supply chain of IMP. The timing of the event will be taken as the date of permanent discontinuation of IMP recorded in the eCRF.

THIS DOCUMENT CONTAINS CONFIDENTIAL INFORMATION AND MUST NOT BE COPIED OR MADE AVAILABLE TO ANY THIRD PARTY WITHOUT THE PRIOR WRITTEN CONSENT OF THE LEO PHARMA GROUP

Unblinding of subject: This event occurs at the first instance of either

- a) Subject self-injecting IMP at home as part of the COVID-19 pandemic contingency plan ([Appendix 6](#)), or
- b) Subject becoming accidentally unblinded

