5.3 Intercurrent events

An intercurrent event refers to a post-randomisation event that either precludes the existence of or affects the interpretation of the measurements of an endpoint. For the purposes of this trial, we define the following 3 intercurrent events:

- **Permanent discontinuation of IMP independent of pandemic restrictions:** This event occurs when a subject permanently discontinues IMP for reasons not related to COVID-19 pandemic restrictions. Permanent discontinuation of IMP due to sickness with COVID-19 (an AE) will be interpreted as permanent discontinuation of IMP independent of pandemic restrictions. This event can occur either at the subject's own initiative or at the investigator's or sponsor's discretion.

Derivation of events from data: This event will be taken to have occurred if the data recorded in the 'End of treatment' eCRF form fulfil all of the following.

- 'Has the subject completed the treatment period?' is answered 'No'
- 'Primary reason for permanent discontinuation from IMP?' is not answered 'Death' or 'Lost to follow-up'
- 'Was the decision to permanently discontinue IMP related to COVID-19 pandemic restrictions?' is not answered 'Yes'.

The timing of the event will be taken as the reported 'Date of last administration of IMP'.

- **Permanent discontinuation of IMP due to pandemic restrictions:** This event occurs when a subject permanently discontinues IMP for reasons related to COVID-19 pandemic restrictions. Permanent discontinuation of IMP due to sickness with COVID-19 (an AE) will not be interpreted as permanent discontinuation of IMP due to COVID-19 pandemic restrictions. Examples of permanent discontinuation of IMP due to pandemic restrictions

THIS DOCUMENT CONTAINS CONFIDENTIAL INFORMATION AND MUST NOT BE COPIED OR MADE AVAILABLE TO ANY THIRD PARTY WITHOUT THE PRIOR WRITTEN CONSENT OF THE LEO PHARMA GROUP

are quarantines, travel limitations, subject being unable or unwilling to travel to site due to personal pandemic-related reasons, site closures, reduced availability of site staff, and interruptions to supply chain of IMP.

Derivation of events from data: This event will be taken to have occurred if the data recorded in the ‘End of treatment’ eCRF form fulfil all of the following.

- ‘Has the subject completed the treatment period?’ is answered ‘No’
- ‘Primary reason for permanent discontinuation from IMP?’ is not answered ‘Death’ or ‘Lost to follow-up’

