Notes: Subject 1 completes the treatment period, subject 2 permanently discontinues IMP independent of pandemic restrictions, subject 3 permanently discontinues IMP due to pandemic restrictions, while subject 4 becomes unblinded and subsequently permanently discontinues IMP independently of pandemic restrictions.

Depending on the estimand strategy selected, the occurrence of an intercurrent event may be ignored, lead to exclusion of data observed after the occurrence of the event, become a component in the definition of the endpoint, or restrict the relevant observation window to the time prior to the occurrence of the intercurrent event. Unblinding and permanent discontinuation of IMP – either independent of pandemic restrictions or due to pandemic restrictions – may occur to the same subject. If these intercurrent events occur on the same date, permanent discontinuation of IMP will be assumed to have occurred first. If an intercurrent event occurs on

THIS DOCUMENT CONTAINS CONFIDENTIAL INFORMATION AND MUST NOT BE COPIED OR MADE AVAILABLE TO ANY THIRD PARTY WITHOUT THE PRIOR WRITTEN CONSENT OF THE LEO PHARMA GROUP

the same date as an endpoint assessment the endpoint assessment will be assumed to have occurred first.

The number and percentage of subjects experiencing intercurrent events will be summarised by visit week interval for each treatment group.

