The primary estimand associated with this endpoint can be seen to assess the difference in the rate of achieving PASI 100 response at Week 16 without permanently discontinuing IMP regardless of subjects becoming unblinded, if permanent discontinuation of IMP due to pandemic restrictions would not occur. In the following, we elaborate on the estimand strategy specified in [Panel 11](#) for this estimand, specifically the strategies for addressing the two intercurrent events related to permanent discontinuation of IMP.

To elaborate on the ‘composite’ strategy for addressing permanent discontinuation of IMP independent of pandemic restrictions, we specify the composite variable to be used for analysis. This variable can take the values:

- “1” if the subject is a PASI 100 responder at Week 16 and has not permanently discontinued IMP independently of pandemic restrictions by Week 16.
- “0” if the subject is a PASI 100 non-responder or has permanently discontinued IMP independently of pandemic restrictions prior to Week 16.

We now elaborate on the ‘hypothetical’ strategy for addressing permanent discontinuation of IMP due to pandemic restrictions. For subjects who have permanently discontinued IMP due to pandemic restrictions prior to Week 16, data collected after permanent discontinuation of IMP will be excluded from analysis and replaced by model-based predictions. The purpose is to predict what value the estimand’s variable would take if the given subject would not permanently discontinue IMP due to pandemic restrictions. With this purpose in mind, two questions naturally arise because of the ‘composite’ strategy for addressing permanent discontinuation of IMP independent of pandemic restrictions:

- a) Would the subject still have been on treatment at Week 16 as opposed to having permanently discontinued IMP independently of pandemic restrictions beforehand?
- b) If yes, would the subject have been a PASI 100 responder at Week 16?

THIS DOCUMENT CONTAINS CONFIDENTIAL INFORMATION AND MUST NOT BE COPIED OR MADE AVAILABLE TO ANY THIRD PARTY WITHOUT THE PRIOR WRITTEN CONSENT OF THE LEO PHARMA GROUP

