5.4.2.2 Sensitivity analyses

5.4.2.2.1 Robustness with respect to intermittent follow-up

For a given subject in the main analysis, the time to response while remaining on treatment is imputed using the scheduled timing of the visit where the desired response is first observed. In order to assess the robustness of the results of the main analysis with respect to this imputation strategy, the probability of achieving a response prior to discontinuation of IMP independent of pandemic restrictions will be estimated based on the multi-state model illustrated in [Panel 16](#).

Panel 16. Multi-state model for the sensitivity analysis accounting for the intermittent nature of the observation process

Abbreviations: IMP = investigational medicinal product.

For this analysis, we formulate the likelihood function for an intermittently observed continuous-time Markovian 3-state process $\{Z(t) | 0 \leq t\}$ in terms of its transition probabilities, as in [\(3\)](#). Given a subject-specific vector of time-fixed covariates \mathbf{x} and states j, k of the 3-state process, the transition probability

$$p_{jk}(s, t | \mathbf{x}) = \text{Prob}\{Z(t) = k | Z(s) = j, \mathbf{x}\}$$

is the probability that a subject in state j at time s will be in state k at time t for $0 \leq s \leq t$.

Letting n denote one of the N randomised subjects in the trial we let

THIS DOCUMENT CONTAINS CONFIDENTIAL INFORMATION AND MUST NOT BE COPIED OR MADE AVAILABLE TO ANY THIRD PARTY WITHOUT THE PRIOR WRITTEN CONSENT OF THE LEO PHARMA GROUP

$$0 = v_{n,0} < v_{n,1} < \dots < v_{n,M_n} \leq 28$$

denote the (potentially subject-specific) inspection times, measured in weeks after randomization, and we let

$$z_{n,0}, z_{n,1}, \dots, z_{n,M_n}$$

denote the states observed for the subject at these times. A subject could be observed to be a non-responder (or responder) and permanently discontinue IMP independently of pandemic restrictions at one and the same visit, say at the Week 20 visit. Such a situation will be interpreted as observing the subject to be in the ‘Non-responder (Randomised)’ (or ‘Responder’) state at the inspection time 20 weeks and observing the subject to be in the ‘Permanent discontinuation of IMP independent of pandemic restrictions’ state at the inspection time 20.1 weeks.

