5.7 Interim analysis

No interim analysis is planned.

THIS DOCUMENT CONTAINS CONFIDENTIAL INFORMATION AND MUST NOT BE COPIED OR MADE AVAILABLE TO ANY THIRD PARTY WITHOUT THE PRIOR WRITTEN CONSENT OF THE LEO PHARMA GROUP

6 Changes to analyses described in the protocol

[Panel 22](#) summarises the changes to the analyses planned in the protocol.

Panel 22. Changes to analyses planned in the protocol

Section in CTP	Description of change	Brief rational
6 Trial objectives, endpoints, and estimands	
Panel 1 lists the additional exploratory endpoints,
 
 Having PASI 100 response, assessed separately at Weeks 1, 2, 6, 10, 12, and 14, Having IGA of 0, assessed separately at Weeks 4, and 8, Having IGA of 0 or 1, assessed separately at Weeks 4, and 8, Having IGA of 0 or 1 and at least a 2-grade improvement from baseline, assessed separately at Weeks 4, and 8, 
which are not described in the CTP.
 
Analyses of the above mentioned endpoints have been specified to be carried out in Panel 10.
	The additional exploratory endpoints, and the analyses of them, have been specified to obtain additional insights from the collected data on the onset of action for the IMPs.

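### SAP 5.3 dates a stop of IMP at the last injection, undeclared in Panel 22, so a responder assessed and then stopped before that visit's dose counts as a failure

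*SAP*

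**What the plan says.** **Event date.** Protocol 14.3.6.1 says of both discontinuation events: "The timing of the event will be taken as the date of permanent discontinuation of IMP recorded in the eCRF". SAP 5.3, under the derivation of events from data, says of both: "The timing of the event will be taken as the reported 'Date of last administration of IMP".

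**Declared changes.** SAP Section 1 sends the reader to Section 6 for departures from the protocol. Panel 22 there "summarises the changes to the analyses planned in the protocol". No row concerns the dating of intercurrent events.

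**Composite.** In SAP 5.4.1, value 1 goes to a Week 16 PASI 100 responder who "has not permanently discontinued IMP independently of pandemic restrictions by Week 16". Value 0 goes to a non-responder or a subject who "has permanently discontinued IMP independently of pandemic restrictions prior to Week 16". Protocol 14.3.6.2 words it the same way.

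**Ordering rules.** SAP 5.3 adds a tie rule, absent from the protocol, for an event on "the same date as an endpoint assessment the endpoint assessment will be assumed to have occurred first". In SAP 5.4.2.2.1, a subject may be seen as a responder and "permanently discontinue IMP independently of pandemic restrictions at one and the same visit"; the response is then placed at 20 weeks and the stop at 20.1 weeks.

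**Visit sequence.** Protocol 9.2 puts all other visit activities before the injection. Protocol 7.1 gives brodalumab in Arm 1 and dummy 2 in Arm 2 at Weeks 0, 1 and 2 and then every 2 weeks to Week 26. Protocol Panel 6 and Section 13.1 count the dummies as IMP.

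**The concern.** The event date decides two things: whether a Week 16 responder counts in the primary composite, and whether a first PASI 100 response comes before or after the competing event in the key secondary analysis.

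A stop after assessment but before dosing is a foreseen situation. The C-SSRS and PHQ-8 are reviewed before that day's injection (protocol 11.5.2 and 11.5.3) and can require IMP to be stopped (10.2.1). Footnote 2 to protocol Panels 2 and 3 provides for a stop at a scheduled visit. For such a subject the last injection belongs to the previous visit, so the SAP date falls before an assessment that was actually made first. The tie rule cannot correct this, because the two dates are no longer equal.

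The reclassified responder has the same scheduled exposure at the Week 16 assessment as a responder who continues: both were last injected at about Week 14. Only what happens after the assessment differs.

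**Working it through.** **1. Size of the back-dating.** Counting 7 days per week, Week 14 is Day 98 and Week 16 is Day 112, a gap of 14 days. With ±3-day windows the range is (112 − 3) − (98 + 3) = 8 days to (112 + 3) − (98 − 3) = 20 days.

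**2. Scores for a subject with PASI 100 observed on Day 112 and a non-pandemic stop.**

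| Case | Last injection | Score, SAP date | Score, stop date plus SAP tie rule |
|---|---|---|---|
| Stopped at Week 16 before the dose | Day 98 | 0 | 1 |
| Week 16 dose given, then stopped | Day 112 | 1 | 1 |
| Week 16 dose held, stopped at Week 18 | Day 98 | 0 | 1 |
| Stopped on Day 105 | Day 98 | 0 | 0 |

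The rules differ only where the Week 16 dose was not given and the stop came at or after the Week 16 assessment. For a pandemic-related stop, SAP dating would instead cause the observed Week 16 PASI to be discarded and imputed.

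**3. The plan's own figure.** Protocol 14.1, scenario e/e′, gives the Week 16 rate as λ01/(λ01 + λ10) × (1 − exp(−(λ01 + λ10) × 16)):

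- brodalumab: 0.0333/0.0605 × (1 − exp(−0.0605 × 16)) = 34.1%, or 41.0 responders of 120
- guselkumab: 0.0158/0.0593 × (1 − exp(−0.0593 × 16)) = 16.3%, or 19.6 responders of 120

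Exact enumeration of the two-sided Fisher test at 5% with 120 per arm gives 86.9% power. Panel 20 states 87.0%, so the figure reproduces.

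**4. Illustration for the primary endpoint.** The numbers affected are assumptions.

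- One responder moves its arm by 1/120 = 0.83 points, or 1/60 = 1.67 points if an arm had only 60 subjects (an assumed size).
- 2% of responders in both arms: 33.5% vs 16.0%, power 85.9%.
- One brodalumab responder only: 34.1% − 0.83 points = 33.3%, power 83.7%.
- One guselkumab responder only: 16.3% − 0.83 points = 15.5%, power 90.2%.

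**5. Illustration for the key secondary endpoint.** Of the 15 post-baseline visits, 14 (Weeks 1, 2, 4, …, 26) are dosing visits. Under the same model, a non-responder is a responder at the next 2-week visit with probability 0.0333/0.0605 × (1 − exp(−0.0605 × 2)) = 0.0627 on brodalumab and 0.0158/0.0593 × (1 − exp(−0.0593 × 2)) = 0.0298 on guselkumab. If 6 not-yet-responders per arm (5% of 120) stopped before a dose, the expected loss is 6 × 0.0627 = 0.38 and 6 × 0.0298 = 0.18 first responses. The expected totals by Week 28 are 59.7% × 120 = 71.6 and 34.6% × 120 = 41.5.

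**The case against.** **The SAP may only be making the protocol operational.** The eCRF is not among the documents. Protocol 11.6.1 ties the end-of-treatment form to the last administration and names no separate discontinuation date. If that is the only date field, SAP 5.3 is a natural translation. This stands, and nobody can infer from these documents that a better recorded date was set aside. The wording still differs without being declared, and the ordering problem remains either way.

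**A reader might infer that the protocol's date alone yields a 1.** It does not for a stop at the Week 16 visit. Such a responder arguably fails value 1, which requires no stop by Week 16, yet does not meet value 0, which requires a stop before it. The protocol has no tie rule. The 1 comes from combining the stopping-visit date with the SAP's tie rule.

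**A reader might infer a contradiction with protocol 10.3**, which says "Subjects who permanently discontinue IMP at Week 16 (Visit 11) or hereafter will be asked to attend at least" an early termination visit. That passage governs attendance, not event dating, and does not settle the score.

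**The tie rule and the multi-state analysis are not literally contradicted.** Both work as written when that visit's dose was given. This is correct. The point is that the SAP's chosen order, response first, is lost when the dose was not given.

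**Dating every stop at the decision has its own cost.** After a held dose (protocol 10.2.2), a response seen after missed injections would count as on-treatment. This also stands, and it is why the remedy should be narrow.

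**Some outputs would show affected subjects.** The Week 16 waterfall plot highlights subjects with prior intercurrent events, and the first supplementary estimand counts their responses. That estimand also restores responders who stopped earlier, so no planned analysis isolates this effect.

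**Conclusion.** The point holds in a narrow form. Followed literally, SAP 5.3 turns an observed Week 16 PASI 100 responder who is stopped at that visit before dosing, for a non-pandemic reason, into a failure. It also lets the competing event pre-empt a first response seen at any such visit. The departure from protocol 14.3.6.1 is not declared.

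The group is small: the subject must be completely clear, stopped at the visit and not yet dosed. Subjects stopped at Week 16 for lack of response score 0 under either rule. No counts are given. The trial also ended ahead of schedule (Panel 22) and its final size is not stated, so the power figures at 120 per arm show scale only.

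A reader might infer that the rule favours one arm. The documents do not support this: both arms have two-weekly injections, and the direction depends on where the affected subjects fall. For the key secondary endpoint, even 6 pre-dose stops per arm would cost well under one expected first response in either arm. The correction is worth making because it is cheap while the trial is blinded, not because a large bias has been shown.

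**What to change.** Before unblinding:

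1. State in SAP 5.3 that when IMP is permanently stopped at an assessment visit before that visit's dose, the event is dated at that visit, so that its assessments come first under the existing tie rule.
2. Apply this date to both the composite variable and the time-to-event analysis.
3. State how the event is dated when a dose is held at one visit and IMP is permanently stopped later.
4. Align the two Week 16 phrases in the composite definition of SAP 5.4.1 with the tie rule, so that a stop at the Week 16 visit has one defined score.
5. List the departure from protocol 14.3.6.1 in Panel 22, with the reason and the eCRF field used.

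The cost is a few sentences and the re-derivation of one event date; no new data collection is proposed. For subjects stopped at a visit before dosing, the change can only add observed responses. Data admitted by the later dates would also enter the imputation models.

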Here, a) will be assumed to have occurred at the first instance, where a remote visit including dispensation of IMP is performed and b) will be taken to have occurred when accidental unblinding of a subject is reported in a protocol deviation. The timing of the intercurrent event will be taken as whichever comes first of the visit date of the first remote visit including dispensation of IMP as recorded in the eCRF or the date of accidental unblinding as reported for the subject in a protocol deviation.

Note, there is a distinction between permanent discontinuation of IMP (an intercurrent event) and withdrawal from trial and/or loss to follow-up. Withdrawal from trial and loss to follow-up, which are not intercurrent events, will be addressed when specifying methods and/or assumptions for handling missing data. The death of a subject has not been described above as an intercurrent event since occurrences of this event are considered unlikely in the setting of this trial. Should it happen that a subject die, then analyses will handle this using the same strategy as described below for addressing permanent discontinuation of IMP due to pandemic restrictions.

Strategies for handling intercurrent events

The ‘hypothetical’ strategy attempts to quantify the effect of treatment, in the hypothetical situation, where intercurrent events do not occur.

The ‘treatment-policy’ strategy attempts to quantify the effect of the decision to treat subjects with the randomised treatment, thus ignoring the occurrence of intercurrent events.

A ‘composite’ strategy accounts for the occurrence of intercurrent events, through the definition of a suitable composite endpoint, whose components include the aforementioned intercurrent events, as well as the endpoint of interest.

A fourth strategy, for addressing intercurrent events, is the ‘while on treatment’ strategy. This strategy will be implemented to handle intercurrent events for time-to-event endpoints. Under the ‘while on treatment’ strategy, interest lies in assessing the treatment response prior to the occurrence of intercurrent events. The occurrence of intercurrent events can then be accounted for through the formulation of a competing risks model.

THIS DOCUMENT CONTAINS CONFIDENTIAL INFORMATION AND MUST NOT BE COPIED OR MADE AVAILABLE TO ANY THIRD PARTY WITHOUT THE PRIOR WRITTEN CONSENT OF THE LEO PHARMA GROUP

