- ‘Was the decision to permanently discontinue IMP related to COVID-19 pandemic restrictions?’ is answered ‘Yes’.

The timing of the event will be taken as the reported ‘Date of last administration of IMP’.

- **Unblinding of subject:** This event occurs at the first instance of either

- I) Subject self-injecting IMP at home as part of the COVID-19 pandemic contingency plan (CTP Appendix 6), or
- II) Subject becoming accidentally unblinded.

Derivation of events from data: I) will be taken to have occurred at (scheduled or unscheduled) visits fulfilling both conditions,

- ‘Type of visit’ is answered ‘Remote visit due to COVID-19 pandemic restrictions’ in the ‘Visit’ or ‘Visit (Unscheduled)’ form
- ‘Number IMP(s) dispensed according to IRT system’ is not answered ‘0’ in the ‘IMP Compliance, Dispensation and Administration’ form.

II) will be taken to have occurred when unblinding of a subject is reported for a visit in a protocol deviation. Instances of II) will be identified by evaluating the descriptions for all the trial’s protocol deviations.

[figure not shown]
THIS DOCUMENT CONTAINS CONFIDENTIAL INFORMATION AND MUST NOT BE COPIED OR MADE AVAILABLE TO ANY THIRD PARTY WITHOUT THE PRIOR WRITTEN CONSENT OF THE LEO PHARMA GROUP

The timing of the intercurrent event will be taken as the earliest 'Visit date' where either I) or II) has occurred.

Note, there is a distinction between permanent discontinuation of IMP (an intercurrent event) and withdrawal from trial and/or loss to follow-up. Withdrawal from trial and loss to follow-up, which are not intercurrent events, will be addressed when specifying methods and/or assumptions for handling missing data. The death of a subject has not been described above as an intercurrent event since occurrences of this event are considered unlikely in the setting of this trial. Should it happen that a subject dies, then analyses will handle this using the same strategy as described below for addressing permanent discontinuation of IMP due to pandemic restrictions.

Journeys of 4 subjects from randomisation to primary endpoint visit are illustrated in [Panel 9](#).

Panel 9: Examples of subject journeys with respect to intercurrent events

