5.4.1 Primary estimand for binary endpoints

For the primary estimands associated with binary endpoints, [Panel 11](#) provides an overview of those strategies that are specified in [Panel 2](#) for addressing each of the intercurrent events described in section [5.3](#).

Panel 11. Intercurrent events strategies for primary estimands associated with binary endpoints

Type of endpoint	Estimand	Strategy for addressing IE		
		Permanent discontinuation of IMP independent of pandemic restrictions	Permanent discontinuation of IMP due to pandemic restrictions	Unblinding of subject
Binary based on investigator assessments	Primary	‘Composite’: The IE is incorporated as a component in a composite variable with the endpoint of interest	‘Hypothetical’: Data collected after occurrence of the IE will be excluded. Resulting missing data will be imputed from a controlled multiple imputation algorithm	‘Treatment-policy’: Occurrences of the IE will be ignored
Binary based on subject assessments	Primary	‘Composite’: The IE is incorporated as a component in a composite variable with the endpoint of interest	‘Hypothetical’: Data collected after occurrence of the IE will be excluded. Resulting missing data will be imputed from a controlled multiple imputation algorithm	‘Hypothetical’: Data collected after occurrence of the IE will be excluded. Resulting missing data will be imputed from a controlled multiple imputation algorithm

Abbreviations: IE = intercurrent event; IMP = investigational medicinal product.

As seen in [Panel 11](#) the strategy for addressing unblinding of subjects will depend on whether the endpoint of interest is based on subject assessments or investigator assessments. In addition, the controlled multiple imputation algorithm, referred to by [Panel 11](#), will depend on the scale for the endpoint of interest (continuous vs. ordinal). This will be elaborated on below.

THIS DOCUMENT CONTAINS CONFIDENTIAL INFORMATION AND MUST NOT BE COPIED OR MADE AVAILABLE TO ANY THIRD PARTY WITHOUT THE PRIOR WRITTEN CONSENT OF THE LEO PHARMA GROUP

Binary endpoints based on investigator assessments

For ease of explanation, we first consider a specific binary endpoint based on continuous investigator assessments, namely the primary endpoint of the trial:

- Having PASI 100 response at Week 16

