The primary estimand for binary endpoints based on subject assessments can be seen to assess the difference in rate of achieving response without permanently discontinuing IMP, if permanent discontinuation of IMP due to pandemic restrictions and unblinding of subjects would not occur. In accordance with [Panel 11](#), this estimand will address unblinding of subjects by the same ‘hypothetical’ strategy as used for addressing permanent discontinuation of IMP due to pandemic restrictions. This means that the above elaboration on estimand strategy also applies to the primary estimand for binary endpoints based on subject assessments with the exception that unblinding of subjects will be handled just as permanent discontinuation of IMP due to pandemic restrictions. Note that when imputing missing response values for binary endpoints based on DLQI, say ‘Having DLQI total score of 0 or 1 at Week 16’, the underlying DLQI total scores will be considered as continuous, cf. [Panel 10](#). At each step of the procedure for imputing underlying DLQI total scores, imputed scores will be rounded to the nearest integer within the range from 0 to 30.

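### The SAP dates accidental unblinding by visit instead of by its reported date, so unblinding that precedes a visit's questionnaires is misdated or undated, and Panel 22 does not declare the change

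*SAP*

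**What the plan says.** Both documents define unblinding as the first of two occurrences: home self-injection under the pandemic plan, or accidental unblinding. They differ on how the second is dated.

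- Protocol 14.3.6.1 takes the earlier of the first remote visit with IMP dispensed and "the date of accidental unblinding as reported for the subject in a protocol deviation".
- SAP 5.3 says that accidental unblinding "will be taken to have occurred when unblinding of a subject is reported for a visit in a protocol deviation". For both routes, "The timing of the intercurrent event will be taken as the earliest 'Visit date' where either I) or II) has occurred".
- SAP 5.3 also has a general tie rule: for an intercurrent event on "the same date as an endpoint assessment the endpoint assessment will be assumed to have occurred first".

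What hangs on the date depends on the endpoint. For binary endpoints scored by the subject, SAP 5.4.1 states that "unblinding of subjects will be handled just as permanent discontinuation of IMP due to pandemic restrictions", so later data are removed and imputed. SAP 5.4.3 does the same for continuous subject-scored endpoints, and SAP 5.5.2 for the second supplementary estimand of the primary endpoint. For the primary estimands of investigator-assessed and time-to-event endpoints, the entry for unblinding in SAP Panels 11 and 14 is "Occurrences of the IE will be ignored".

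SAP Section 1 refers the reader to Section 6 for departures from the protocol analyses. Panel 22 in that section has no entry on dating unblinding.

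**The concern.** The protocol (14.3.6.1) treats unblinding as something that can change the meaning of patient-reported outcomes. That is why the primary estimands for DLQI, SF-36v2, itch and pain exclude what follows it. The exclusion works only if the event is dated no later than the first affected answer.

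The SAP allows a visit date only and then places that visit's assessments before the event. If a subject learns the allocation between two visits and the deviation is attached to the later one, the questionnaires at that visit and the diary entries in between pass as blinded. If the phrase means only the visit at which unblinding occurred, unblinding between visits has no date at all. The SAP does not say which meaning applies, although its introduction says that its detail should let a reader reproduce every analysis.

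**Working it through.** The plan gives no figure on this point to reproduce. The check sets the two rules side by side and then does a day count.

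**Inputs.** Randomisation is Day 1 (SAP 5.1), and I take the nominal visit day as 7 × week + 1. Visits fall at Weeks 0, 1, 2, 4 and then every 2 weeks to 28, which gives two 7-day and thirteen 14-day intervals: 2 × 7 + 13 × 14 = 196 days. DLQI is collected after baseline at Weeks 4, 8, 12, 16, 20, 24 and 28, and SF-36v2 at Weeks 4, 8, 16 and 28 (protocol Panels 2 and 3). The itch and pain weekly averages are analysed at Weeks 4, 8, 16 and 28, each needs at least 4 days of data, and the Week 4 window is Days 22 to 28 (SAP 5.1, Panel 7). DLQI, SF-36v2 and PHQ-8 come before the investigator, safety and C-SSRS assessments (protocol Section 4, note 8). All other visit activities come before the injection (protocol 9.2).

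**The two rules by timing of the event**

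| Unblinding occurs | Protocol date | SAP date | Result under the SAP |
|---|---|---|---|
| At the injection of the visit it is reported for | That day | That day | Order correct; questionnaires came first |
| Between visits, attached to the next visit | Actual day | Next visit | One set of questionnaires and the intervening diary days kept |
| At the visit, before its questionnaires | That day | That day, assessments first | Questionnaires kept |
| Between visits, if only the visit of occurrence counts | Actual day | None | Event undated |

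**Example.** Unblinding is on Day 16 and is reported for the Week 4 visit, Day 7 × 4 + 1 = 29. The lag is 29 − 16 = 13 days. The SAP keeps the Week 4 DLQI and SF-36v2 and diary Days 17 to 28, including all 7 days of the Week 4 window. The protocol date would exclude them.

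**Largest lag.** On the nominal schedule it is 14 − 1 = 13 days. With both ±3-day windows stretched it is 14 + 6 − 1 = 19 days. Everything after the linked visit is excluded under either rule.

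**How often it would touch an endpoint.** Assume unblinding falls uniformly over the 196 days and is attached to the next visit.

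- Mean lag: (2 × 7²/2 + 13 × 14²/2) / 196 = (49 + 1274) / 196 = 6.75 days.
- Next visit has a DLQI: 7 × 14 / 196 = 98/196 = 50%.
- Next visit has an SF-36v2: 4 × 14 / 196 = 56/196 = 29%.
- At least 4 unblinded days in an analysed itch or pain week: the event must fall in the first 10 days of the 14-day interval before one of four visits, 4 × 10 / 196 = 20%.

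Counting only whole days strictly between visits (2 × 6 + 13 × 13 = 181 days) gives 91/181 = 50%, 52/181 = 29% and 36/181 = 20%.

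**Effect per subject.** At the planned 120 per arm, one subject moves a DLQI 0/1 rate by at most 1/120 = 0.8 percentage points. This is an upper bound, because the alternative to keeping the value is imputing it, not reversing it. SAP Panel 22 reports that the trial ended ahead of schedule, so the weight per subject would be larger if fewer were randomised.

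**The case against.** The strongest defence is that the phrase most naturally means the visit where unblinding happened, and that nothing in the SAP moves an event forward to the next visit. On-site risk is concentrated at the injection, which is why protocol 9.3.1 has subjects blindfolded during administration. Home self-injection is captured by its own route. At the injection the visit date is the true date, and assessment-first is the true order.

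This defence holds for that case, which is the main one the procedures foresee. A reader might infer that the SAP rule keeps unblinded patient-reported data in general; the documents do not support that. The error needs unblinding between visits, or at a visit before its questionnaires, and the documents report no instance of either. The defence does not remove the difference from the protocol, and on its own reading a between-visit event has no date.

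A reader might also infer a larger diary effect. The lag is at least 4 days in (2 × 3 + 13 × 10) / 196 = 69% of uniformly timed events, but most of those days lie outside the four analysed weeks; the relevant share is 20%. Uniform timing is itself unsupported and serves only to show scale.

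The consequences beyond patient-reported endpoints are thin. In the second supplementary estimand, the score kept is a PASI from a blinded assessor, which the protocol expects to be unaffected. The 'blinded' C-SSRS and PHQ-8 periods probably use the same date, but protocol 14.3.9.5 and 14.3.9.6 do not define when they end, so that link is an inference.

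**Conclusion.** The protocol and SAP date accidental unblinding differently, and the SAP does not declare it. The effect is conditional and small: per affected subject, at most one set of on-site questionnaires and up to about two weeks of diary data on the nominal schedule.

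The reach is the subject-assessed secondary and exploratory endpoints and the second supplementary estimand of the primary endpoint. It would be wrong to infer any threat to the confirmatory results, because the primary estimands for PASI 100 at Week 16 and time to PASI 100 disregard unblinding. The percentages rest on the assumed uniform timing and on attachment to the next visit. The number of affected subjects is not given and may be zero. This is a minor point, but it concerns a stated rule that departs from the protocol's estimand, which is more than a missing detail.

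**What to change.** In SAP 5.3:

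- Date accidental unblinding by the date in the protocol deviation, as in protocol 14.3.6.1. Use the visit date only when no date is recorded.
- Do not apply the assessment-first tie rule when the deviation shows that unblinding came before that visit's assessments.
- If the visit-date rule is kept, declare and justify it in Panel 22, and state what being reported for a visit means.

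The cost is a sentence or two in the SAP and a date looked up in deviation descriptions that SAP 5.3 already commits to evaluating in full. No confirmatory analysis changes.
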